- To compare the genomic damage in both types of iron supplementation.

Study hypothesis

Weekly ferrous sulfate supplementation will be more effective in the prevention of IDA in infants than daily supplementation due to a higher adherence and a lower incidence of adverse effects. Weekly iron supplementation will cause less genomic instability as compared with daily iron supplementation.

Study design

Randomized controlled clinical trial.

Study sample

Eligibility

Infants performing monthly health controls at the Pediatric Health Observatory of IDIP, La Plata Children's Hospital, from birth to six months of age will be included in the study.

Inclusion, exclusion and elimination criteria

Inclusion criteria: Three-month-old clinically healthy breastfeeding infants with birth age > 37 weeks, birth weight between 2500 and 4000 g, a normal fetal and neonatal history, that attend IDIP's Health Observatory and whose parents/guardians express the will to participate in the study and sign a written informed consent form.

Exclusion criteria: Anemic and/or iron deficient infants or with chronic diseases or acute infections or under antibiotic/vitamin treatment within 15 days prior to the study.

Elimination criteria: infants with severe intolerance to iron preventive supplementation, who will receive the alternative preventive treatment with ferrous fumarate or iron polymaltose complex).

Unit of analysis: Three to six month-old infants.

Sample size and selection

According to ENNyS, the prevalence of anemia in 6-9 months old infants is 50.8%. Our controlled interventions would reduce such prevalence to 30%. Sample size was estimated with 0.95 significance level and 0.80 power, resulting in 174 infants (n= 87 for each supplementation group). This number was adjusted considering a 15% dropout, thus enrolling 204 infants.

Methods

Operational definition of variables

Main variables

-Anemia is defined as the “decrease in the total amount of blood cells or a blood hemoglobin (Hb) concentration more than 2 standard deviations below the mean of an age- and sex-matched reference range”. We will define the presence of anemia when Hb < 9.5 g/dL at 3 months of age and Hb < 11.0 g/dL at six months of age (CDC, 2007).

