-Iron deficiency is defined as insufficient iron in the body. It will be considered when blood ferritin <12 ng/ml (WHO 2001). Since ferritin is an acute phase reactant, we will measure C-reactive protein (CRP) to assess an eventual inflammatory state. When CRP is ≥ 5 mg/L, ID will be defined by a blood ferritin <30 ng/ml. The soluble transferrin receptor (sTfR) which is not influenced by inflammation will also be used (cut-off value, sTfR 8.3 mg/L) (Grant 2012).

Secondary variables

-Adverse effects: presence (or absence) and frequency of one or more of the following effects during ferrous sulfate supplementation (rejection, constipation, vomiting, diarrhea, abdominal pain).

-Adherence to treatment: is the rate of adherence to medication intake, dietary plan or lifestyle changes according to recommendations agreed on with healthcare professionals (OMS, 2003).

Adherence will be measured with the formula:

$$\frac{(\text{ml SO}_4\text{Fe received} - \text{ml SO}_4\text{Fe remaining})}{\text{days between the medication vial delivery and its return}} \times 100$$

where ml SO₄Fe received is the volume of ferrous sulfate delivered in a vial, sufficient to cover the prescription until the infants' next control (1 month), and ml SO₄Fe remaining is the residual volume in the vial at the moment of the health control.

We will consider low adherence the consumption of less than 50% of the amount of medication

prescribed for the study period, and less than 50% of intakes prescribed for the study period.

We will consider high adherence consumption of more than 80% of the amount prescribed and more than 80% of the intakes prescribed.

All combinations not covered by low and high adherence will be considered as moderate adherence.

-Genomic instability: Chromosome, DNA and cell damage caused by certain agents. We will evaluate oxidative stress and genomic damage at cytomolecular level and at DNA base level.

- Oxidative stress: imbalance between reactive oxygen species (ROS) production and accumulation and the counteracting enzymatic/non-enzymatic antioxidant mechanisms. We will measure catalase and superoxide-dismutase enzymatic activity and evaluate cell damage by lipid peroxidation through thiobarbituric acid-reactive substances (TBARS) assessment.

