We will also determine the incidence of adverse effects and the incidence of low treatment adherence at six months of age for weekly vs. daily iron supplementation in both EBF and MF and calculate RR (95% CI) at six months of age.

[figure not shown]
Means and differences of enzymatic SOD and CAT activity and TBARS concentration at three and six months will be compared in both study groups. The same will apply to the Comet and 8 oxodG assays. Differences between groups will be determined by Anova or Kruskal-Wallis test for quantitative variables with post-hoc comparisons and Chi-square for categorical variables. Within group comparisons will be analyzed using Student's or Wilcoxon test.

Risk of bias assessment

Selection bias could be present since parents/tutors willing to participate could show higher interest in the research project than those who do not participate. Considering that the population sample attends for monthly controls, a trust relationship may be established between parent/tutor and pediatrician, resulting in a higher degree of adherence to supplementation than in the general population.

Project Schedule

Study flowchart

Work plan

SPECIFIC OBJECTIVE 1: Compare the effectiveness of weekly, daily and no iron supplementation in EBF infants.

SPECIFIC OBJECTIVE 2: Compare the effectiveness of weekly, daily and no iron supplementation in MF infants.

| ACTIVITY | RESPONSIBLE | EXPECTED RESULT |
|--|----------------------------|--|
| Enrollment of infants according to the inclusion criteria. | Pediatricians | Incorporate infants who comply with inclusion criteria |
| Informed consent. | | |
| Intervention assignment. | Statistician | Random allocation |
| Blood sample collection. | Laboratory technician | Adequate specimen collection (enough volume, non clotted) |
| Hemoglobin, ferritin, PCR and sTfR determinations. | Biochemists | Assessment of the prevalence of anemia and iron deficiency |
| Indication for and monitoring of the intervention | Pediatricians | Complete registry of the intervention. |
| Text message reminders | Pediatricians | Intervention adherence. |
| Weight and height measurement. | Pediatrician, Nutritionist | Determine the anthropometric nutritional condition. |
| Registry of data. | Data entry | Complete database. |
| Data analysis and interpretation of results. | Team, Statistician | Report of results and conclusions. |

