SPECIFIC OBJECTIVE 3: Compare the incidence of adverse effects on weekly vs. daily iron supplementation for the prevention of anemia

| | | |
|--|--------------------|--|
| Monitoring of the record of adverse effects. | Pediatricians | Adequate record of the presence and frequency of adverse effects in both types of supplementation. |
| Participant follow-up. | Pediatricians | Early detection of adverse effects that may prevent intervention progression. |
| Control of data record forms | Team | Early detection of adverse effects. |
| Data analysis and interpretation of results. | Team, statistician | Report of results and conclusions. |

SPECIFIC OBJECTIVE 4: Compare the degree of treatment adherence to weekly and daily iron supplementation at six months of age.

| | | |
|---|--------------------|---|
| Monthly control of droppers to calculate adherence | Biochemist | Correct administration of iron supplementation |
| Monitoring of drug intake (registry form and phone calls) | Pediatricians | Adequate drug intake according to prescription. |
| Data analysis and interpretation of results. | Team, statistician | Report of results and conclusions. |

SPECIFIC OBJECTIVE 5: Compare oxidative stress indicators resulting from both forms of iron supplementation.

| | | |
|-------------------------|-----------------------|------------------------------|
| Blood sample collection | Laboratory technician | Adequate specimen collection |
|-------------------------|-----------------------|------------------------------|

| | | |
|---|--------------------------------|---|
| | | (enough volume, non clotted) |
| TBARS, CAT and SOD assessment | Biochemist, IGEVET researchers | Evaluation of oxidative stress |
| Data analysis and interpretation of results. | Team, statistician | Report of results and conclusions. |
| SPECIFIC OBJECTIVE 6: Compare genomic damage with both forms of iron supplementation | | |
| Blood sample collection | Laboratory technician | Adequate specimen collection (enough volume, non clotted) |
| Comet assay | IGEVET researchers | Cytomolecular damage evaluation |
| 8 oxo-dG assessment | IGEVET researchers | Quantification of oxidized bases |
| Data analysis and interpretation of results. | Team, statistician | Report of results and conclusions. |

References

- Aebi H. Catalase in vitro. *MethodsEnzymol* 1984; 105:121-6.

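### The objective is the degree of adherence, but the only adherence comparison named is the relative risk of low adherence, so differences above the 50% cut-off are not analysed

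*Protocol*

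**What the plan says.** The Work plan states specific objective 4 as "Compare the degree of treatment adherence to weekly and daily iron supplementation at six months of age". The Objectives section gives the same aim without the word degree.

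Under Operational definition of variables, Secondary variables, adherence is graded on two measured shares, amount and intakes. Low adherence is defined by "We will consider low adherence the consumption of less than 50% of the amount of medication" prescribed, joined to a second condition: "and less than 50% of intakes prescribed for the study period". At the other end, "We will consider high adherence consumption of more than 80% of the amount prescribed and more than 80% of the intakes prescribed". The rest is the middle class: "All combinations not covered by low and high adherence will be considered as moderate adherence".

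Under Intervention progress monitoring, parents complete a daily or weekly consumption form, and the volume left in the droppers is checked at each monthly visit. Both shares can therefore be computed for each infant.

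In Data analysis, the adherence comparison is "the incidence of low treatment adherence at six months of age for weekly vs. daily iron supplementation in both EBF and MF", reported as a relative risk with a 95% confidence interval. No analysis is named for the high class, the moderate class or either percentage.

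The Study hypothesis expects weekly iron to do better "due to a higher adherence and a lower incidence of adverse effects".

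**The concern.** The named analysis answers a narrower question than the objective asks. It asks whether fewer infants fall below half on both measures. It does not ask how much of the prescribed iron was taken. An infant who moves from moderate to high adherence contributes nothing to the relative risk.

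Two features may keep the low class small in this trial. Both conditions must be met, and families get reminders, weekly contact and monthly visits. The Risk of bias assessment itself expects the relationship with the pediatrician to work in this direction, "resulting in a higher degree of adherence to supplementation than in the general population". If the low class is small, the relative risk will be imprecise although the forms and droppers hold more information.

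Higher adherence is one of the two mechanisms in the hypothesis. An imprecise relative risk would leave that mechanism largely unexamined even if the percentages could have shown a difference.

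**Working it through.** **1. The plan's own figure.** Sample size and selection assumes anemia of 50.8% falling to 30% with 80% power, and states 87 per group. I read the 0.95 significance level as two-sided alpha 0.05. With p̄ = (0.508 + 0.30)/2 = 0.404:

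n = [1.96·√(2·0.404·0.596) + 0.8416·√(0.508·0.492 + 0.30·0.70)]² / 0.208² = (1.360 + 0.571)² / 0.0433 ≈ 86.2, rounded up to 87.

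This matches the stated 87 per group and 174 in all. With 15% dropout, 174/0.85 = 204.7, against 204 stated. No calculation was made for adherence.

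**2. Inputs for adherence.**
- From the protocol: 12 weeks of supplementation, so 12 weekly intakes or 12 × 7 = 84 daily intakes; low means under 50%; 87 per arm with feeding groups pooled.
- Assumed, because the protocol gives none: the daily mean percent taken, a 10-point weekly advantage in that mean, and the between-infant spread.
- Also assumed: 44 per arm within one feeding group, which is an even split of 87. The protocol does not give the split.

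**3. One case by hand (normal model, means 75% and 85%, SD 20).**
- Share low, daily: Φ((50 − 75)/20) = Φ(−1.25) = 10.6%. Weekly: Φ((50 − 85)/20) = Φ(−1.75) = 4.0%.
- Low-adherence comparison: the difference is 0.0656. The null SE is √(2·0.0729·0.9271/87) = 0.0394 and the alternative SE is √((0.0945 + 0.0385)/87) = 0.0391. Power = Φ((0.0656 − 1.96·0.0394)/0.0391) = Φ(−0.30) ≈ 38%.
- Mean percent: SE = 20·√(2/87) = 3.03. Power = Φ(10/3.03 − 1.96) = Φ(1.34) ≈ 91%.
- At 44 per arm the two figures are 22% and 65%.

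**4. Simulation with bounded intakes.** Each infant has a beta-distributed probability of taking an intake. The number taken is binomial out of 12 (weekly) or 84 (daily). There were 4,000 replicates, with a pooled z-test on low adherence and a Welch t-test on percent taken. At means of 75% and 85% and intraclass correlation (ICC) 0.2, the SD of the true proportion is √(0.2·0.75·0.25) = 0.19 daily and √(0.2·0.85·0.15) = 0.16 weekly. Low adherence is then 12.5% and 5.0%. Power is 42% against 93% at 87 per arm, and 27% against 68% at 44.

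With a 10-point gain, ICC 0.1 to 0.3 and 87 per arm:

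| Assumed daily mean | Power, low adherence | Power, mean percent taken |
|---|---|---|
| 70-80% | 11-49% | 75-99% or more |
| 60-65% | 52-68% | 67-97% |
| 50% | 62-91% | 62-94% |

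Simulation error is about ±2 points (2·√(0.25/4000) = 0.016). The low class was simulated on intakes alone. Requiring low volume as well can only make it smaller.

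**5. Second model.** The normal model with daily mean 70-85%, SD 15-30 and a 10-point gain gives 11-50% for low adherence against 59-99% for the mean at 87 per arm. At 44 per arm it gives 8-28% against 35-88%.

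**The case against.** **Low adherence need not be rare.** A reader might infer from the reminders and contacts that few infants can be low. The protocol gives no rate. It calls adherence in the country low, and being higher than in the general population does not establish a daily mean of 75%. This objection stands: rarity is an assumption, and the daily mean drives the result.

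**A 10-point gain would not always be missed.** A reader might infer that it usually would be. At 87 per arm that holds for daily means of about 70% or more. At 60-65% power is above one half, and at 50% the two analyses are nearly equal. If the 10 points are taken as low-adherence incidence instead, 15% against 5% has about 57-60% power at 87 per arm.

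**Large group differences would be found.** It is tempting to say that any contrast above 50% counts as none. That is true of two individual infants, not of arms. Group means of 60% and 85% would be detected through the low class with over 99% power at 87 per arm and 92-96% at 44.

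**The general test sentence may cover adherence.** Data analysis later names ANOVA or Kruskal-Wallis for quantitative variables and chi-square for categorical ones. That sentence follows the biomarkers and does not mention adherence. Reading it to include the three classes is possible but not stated.

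**Adherence is secondary.** The sample size rests on anemia, and adherence is one of two reasons in the hypothesis, not the only one. Limited power on a secondary variable is ordinary, a wide confidence interval would show the imprecision, and low adherence is a legitimate, readable outcome. This limits the weight of the point. It does not explain why the measured percentages have no named comparison when the objective is degree. Nor does the mean cure small strata: at 44 per arm and daily means of 50-65%, it has only 37-76% power.

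**Conclusion.** The mismatch between objective and analysis holds on the text: degree is the aim, percentages are collected, and only the low class is named for comparison. In the ranges tabulated, the mean percent was at least as powerful as the low-adherence comparison. At 87 per arm and a 10-point gain, the loss is large at assumed daily means of 70-80%, moderate at 60-65% and close to nil at 50%. All of these figures depend on assumed means and spread, and the figures at 44 per arm also depend on an assumed even feeding split. The documents do not support saying that low adherence is rare in this trial, that a 10-point gain would usually be missed whatever the adherence level, or that the hypothesis rests on adherence alone. This is a worthwhile, inexpensive improvement to a secondary analysis and does not threaten the main comparison of anemia.

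**What to change.** In Data analysis, make the adherence comparison the weekly-minus-daily difference in mean percent of prescribed intakes taken, and likewise in percent of prescribed volume consumed. Give each with a 95% confidence interval, by feeding stratum and pooled with adjustment for stratum. Define the volume percentage as volume consumed over volume prescribed, because the printed adherence formula divides by days. Keep the relative risk of low adherence and the distribution over the three classes as supporting results.

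The cost is a sentence or two in the protocol and one more table in the report. The consumption forms and monthly dropper checks already supply the data, so no visit, sample or infant is added.

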Finally, micronutrient deficiencies and excess may cause genomic damage, which could be in the same range of magnitude, or even higher, than genomic damage caused by exposure to high doses of environmental genotoxic agents such as carcinogenic agents, ultraviolet radiation and ionizing radiation (Fenech, 2010). Furthermore, since iron is not easily eliminated from the body and participates in the cell redox reactions, where ROS generate through Fenton reactions, increased iron concentrations could damage proteins, lipids and DNA permanently, causing structural and functional impairments. High plasma iron concentrations may amplify the effect of free radicals (Aksu, 2010); although cells have developed different mechanisms to reduce iron toxicity, including the regulation of iron transport through cell membranes and the production of ROS-eliminating enzymes. An imbalance of these systems caused by excess iron could increase oxidative damage susceptibility that could cause an increase in the mutation rate. These could increase the risk of developing neoplastic processes, diabetes and cardiovascular and neurological disease (Evans, 2004; Liu, 2009; Toxqui, 2010).

The effect of treatment with iron on DNA oxidation has been investigated in children with IDA, observing a significant increase of DNA strand breaks and baseline oxidative DNA damage as compared with children not receiving treatment (Aksu, 2010). However, we have not found evidence in the literature about the effect of preventive doses of iron supplementation on DNA. Therefore, we propose to compare the effectiveness of weekly and daily supplementation for the prevention of anemia in infants less than six months of life and to analyze their impact on genomic stability.

Objectives

General: To compare the effectiveness of weekly and daily iron supplementation for the prevention of anemia in infants.

Specific: To compare:

- To compare the effectiveness of weekly, daily and no iron supplementation at six months of age in EBF infants.
- To compare the effectiveness of weekly and daily iron supplementation in six-month-old infants receiving MF.
- To compare the incidence of adverse effects for weekly and daily iron supplementation at six months of age.
- To compare the adherence to treatment of weekly and daily iron supplementation at six months of age.
- To compare the concentration of oxidative stress biomarkers for both types of iron supplementation.

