- Genomic damage: DNA damage assessed by cytomolecular techniques using the Comet assay (damage index assessment in 200 cells, quantifying damage by Tail moment and Olive Tail moment). The frequency of oxidized DNA bases will be determined by competitive 8-oxo-dG Elisa.

Other variables:

- Sex, weeks of gestation, umbilical cord clamping.

- Infant nutritional condition will be assessed by anthropometry (weight, height, head circumference) at three and six months.

- Sociodemographic data of infants and relatives, including place of residence, unsatisfied basic needs, maternal education.

- Maternal nutritional condition will be evaluated with anthropometry and iron status.

- Environmental exposure to genotoxic agents (antibiotics, radiation (X-rays) and chemical substances like pesticides, solvents and industrial waste) will be assessed by questionnaire.

Data collection

-Patient enrolment

During health control visits to IDIP Health Observatory on the first and second month of life, parents and tutors will be invited to participate in the study; the study's protocol, its aims and benefits will be explained in a plain language. They will be asked to sign a written informed consent form in case they accept their children be incorporated to the study. Infants meeting the inclusion criteria with exclusively breastfeeding (EBF) will be randomly divided into three groups: weekly, daily and no supplementation. Those with mixed feeding (breastfeeding and formula; MF) will be randomly divided into two groups: weekly and daily supplementation.

- Intervention

Weekly supplementation (EBF or MF): infants will receive a weekly dose of ferrous sulfate (4mg/kg/week).

Daily supplementation (EBF or MF): infants will receive a daily dose of ferrous sulfate (1 mg/kg/day).

Without intervention (only EBF): infants will receive no supplementation, following the current SAP guidelines. Ferrous sulfate will be supplied by pediatricians.

- Randomization

Randomization will be performed by computer-generated random sequences of numbers in blocks of variable length. Randomization will be stratified by type of intake (EBF or MF).

Treatment assignments will be placed in sequentially numbered, opaque and sealed envelopes which will be consecutively put in a box and later removed one at a time. The person in charge of the random allocation process will not take part in the enrollment process.

- Blinding

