Pediatricians in charge of supplementation will know the assigned intervention only when the envelopes are open. Professionals in charge of performing laboratory tests will not know intervention assignments.

-Sample collection. Surveys

Before supplementation, 3-ml blood samples from infants will be drawn to assess anemia, ID, and genomic stability. All non-anemic/iron deficient infants will be recruited and will be supplemented

according to the group assigned during 12 weeks (three months). At the end of this period (six months of age), blood samples will be drawn again to measure the study variables. Infant and family sociodemographic data will be surveyed at the first visit (three months of age). Anthropometric measurements will be taken at three and six months. Nutritional assessment of the mothers will be performed at the beginning and at the end of the study, measuring weight and height and drawing blood samples for anemia and ID assessment.

- Intervention progress monitoring

Pediatricians will prescribe iron doses and manner of administration. Parents and/or tutors will receive one or more droppers with ferrous sulfate sufficient to complete one-month supplementation, considering that all infants will perform monthly health controls. The Telegram program “LactaPlusIDIPBOT”, designed at IDIP, will be used to send reminders for iron supplement intake. They will be also contacted weekly (Facebook messenger, Whatsapp, Telegram). To monitor adherence, we will use a daily/weekly consumption record form that will be completed by parents/tutors and delivered at each health control. To determine consumption, we will control de excess volume in droppers during each monthly control.

- Record of adverse effects

Parents and/or tutors will receive a form to register adverse effects which will be presented at each monthly control. They will register intake rejection, constipation, vomiting, diarrhea, and abdominal pain. Infants with intolerance to iron supplementation will be excluded from the study but will continue on an alternative treatment (1 mg/kg/day fumarate or iron polymaltose complex).

- Laboratory tests

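### The oxidative-stress and genomic markers are compared between groups without the 3-month value as a covariate; adjusting for it costs nothing and, unless the 3-to-6-month correlation is near 0 or 1, gives tighter estimates

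*Protocol*

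**What the plan says.** The markers are available at two time points. Under Sample collection, the protocol states: "Before supplementation, 3-ml blood samples from infants will be drawn to assess anemia, ID, and genomic stability". It continues: "At the end of this period (six months of age), blood samples will be drawn again to measure the study variables".

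The Data analysis section sets out the comparison: "Means and differences of enzymatic SOD and CAT activity and TBARS concentration at three and six months will be compared in both study groups". For the genomic assays: "The same will apply to the Comet and 8 oxodG assays". The between-group test is then named: "Differences between groups will be determined by Anova or Kruskal-Wallis test for quantitative variables with post-hoc comparisons". Within-group change is tested by Student's or Wilcoxon test. No regression model or covariate is named in that section or elsewhere in the protocol.

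Two design features bear on the remedy. Randomization is stratified by feeding type, exclusive breastfeeding (EBF) or mixed feeding (MF). Only the EBF infants have an untreated arm; they "will be randomly divided into three groups: weekly, daily and no supplementation".

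The question put to the markers is weekly against daily iron. One specific objective reads: "To compare the concentration of oxidative stress biomarkers for both types of iron supplementation". The next asks the same of genomic damage, and the second half of the study hypothesis expects less genomic instability with weekly iron.

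**The concern.** The protocol collects a pre-treatment value of every marker but uses it only through the 3-to-6-month difference. A comparison of 6-month means ignores the baseline. A comparison of change scores subtracts all of it, which over-corrects unless the two visits are almost perfectly correlated. A regression on the 3-month value estimates how much to subtract.

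The trial was sized on anemia and no sample size is given for the markers, yet half of the hypothesis rests on them. Avoidable imprecision would widen the weekly-daily intervals. The plan also produces two between-group results per marker, means and differences, without saying which leads. Which of the two is more precise depends on a correlation that is not known in advance.

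**Working it through.** **The plan's own figure.** The only computed design figure is for anemia: 50.8% against 30%, power 0.80, with the stated 0.95 level read as two-sided alpha 0.05. With pooled variance and no continuity correction:

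n = [1.96·√(2·0.404·0.596) + 0.8416·√(0.508·0.492 + 0.30·0.70)]² / 0.208² = (1.360 + 0.571)² / 0.0433 ≈ 86.2, so 87 per group.

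This matches the protocol's 87 per group and 174 in all. It says nothing about the markers, but it supplies the group sizes used below.

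**Inputs that are assumed.** The correlation r between the 3- and 6-month values is not in the documents, so I use a range. I also assume equal SDs at both visits, a linear relation, and a weekly-daily difference of 0.4 SD for the power figures.

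**Variance of the arm contrast, relative to 6-month means**

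- 6-month means: 1
- change scores: 2(1 − r)
- regression on the 3-month value: 1 − r²

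The last is never larger than the others: 1 − r² ≤ 1, and (1 − r²) / [2(1 − r)] = (1 + r)/2 ≤ 1. This ignores the one or two degrees of freedom spent.

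| r | 6-month means | Change | Adjusted | Variance gain over better planned analysis | Interval narrower by |
|---|---|---|---|---|---|
| 0 | 1 | 2.00 | 1.00 | 0% | 0% |
| 0.1 | 1 | 1.80 | 0.99 | 1% | 0.5% |
| 0.2 | 1 | 1.60 | 0.96 | 4% | 2% |
| 0.3 | 1 | 1.40 | 0.91 | 9% | 1 − √0.91 ≈ 5% |
| 0.5 | 1 | 1.00 | 0.75 | 25% | 1 − √0.75 ≈ 13% |
| 0.7 | 1 | 0.60 | 0.51 | 1 − 0.51/0.60 = 15% | 1 − √0.85 ≈ 8% |
| 0.8 | 1 | 0.40 | 0.36 | 10% | 5% |

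At r = 0.5 the gain equals 1/0.75, or about one third more infants.

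**Power for 0.4 SD**, as Φ(0.4/√(2·factor/n) − 1.96), better planned analysis → adjusted, at r = 0.3 / 0.5 / 0.7:

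- 87 per iron arm (all 174 infants in the two iron arms): 75% → 79%, 75% → 86%, 93% → 96%.
- 174 infants over all five cells, half of them EBF, equal arms within feeding type, weekly against daily pooled; n = 174·(0.5/3 + 0.5/2) = 72.5 per iron arm: 67% → 71%, 67% → 79%, 87% → 92%.
- The same split read within feeding type. EBF, 29 per arm: 33% → 36%, 33% → 42%, 50% → 57%. MF, 43.5 per arm: 46% → 50%, 46% → 58%, 67% → 74%.

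**Simulation check.** With 29 EBF and 44 MF infants per iron arm, a 0.3 SD feeding gap at both visits and 4,000 runs, power at r = 0.3 / 0.5 / 0.7 was 0.716 / 0.789 / 0.920 adjusted, 0.531 / 0.674 / 0.876 for change and 0.670 / 0.661 / 0.651 for 6-month means. Type I error was 0.040 to 0.053 for all three methods. The planned analyses are therefore not biased, and the formulas hold up.

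**The feeding term.** In a pooled model that already contains the 3-month value, adding feeding type changes the standard error by a ratio of only 0.998 / 0.99 / 0.98 for an assumed EBF-MF gap of 0.2 / 0.5 / 0.8 SD. Almost all of the gain comes from the baseline value.

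**The case against.** The planned tests are valid, the outcomes are secondary, and covariates for such outcomes are often left to a statistical analysis plan, which is not at hand. The validity and the secondary status are granted. But the protocol does not leave this method open: it names the tests and the quantities they act on. The point is about that stated choice, and a fuller analysis plan may already improve on it.

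The gain may be small. At r of 0.1 to 0.2 it is negligible. Within 0.3 to 0.7 it is 4, 11 and 3 power points at 87 per arm, so only a correlation near 0.5 brings a sizeable benefit. Variance percentages also look larger than the narrowing of the intervals. All of this stands, and it limits the size but not the direction.

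The power figures use a two-sample normal approximation, not ANOVA with post-hoc tests, and the power of Kruskal-Wallis was not computed. That stands too. The figures are best read as comparisons between methods.

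A regression drops infants without a usable 3-month value, whom a comparison of 6-month means would keep. One 3 ml draw feeds many assays, so this can happen. It needs a rule, given under the fix.

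A reader might also infer that the plan ignores the feeding stratum. The documents do not support that. The Data analysis section speaks of two study groups, first for anemia, where it goes straight on to separate reference categories for EBF and MF, and then for the markers. The phrase can mean EBF and MF analysed separately, or weekly against daily. On the first meaning the stratum is already handled, and only the within-feeding-type power figures describe the plan.

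**Conclusion.** The point holds as a matter of efficiency. Leaving out the 3-month value loses precision on all five markers unless r is near 0 or near 1. Against the better planned comparison, the loss is 9%, 25% and 15% of variance at assumed r of 0.3, 0.5 and 0.7. This rests on equal SDs at the two visits, a linear relation and values of r that the documents do not supply.

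Two stronger conclusions would be wrong. The planned tests are not invalid or biased, since randomization protects them. Nor is a material gain guaranteed for every marker: adjustment is not materially worse at any r, but it may add almost nothing. The change is worth making because it is nearly free and gives one leading result per marker. The primary anemia comparison is unaffected.

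**What to change.** In the Data analysis section, before any marker data are analysed, replace the between-group test for the five markers with a regression of the 6-month value (log-transformed if skewed) on randomized arm and 3-month value. In addition:

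- State whether weekly against daily is pooled across feeding types. In any pooled estimate, include feeding type as a term.
- Report EBF and MF estimates separately as well, since a pooled figure averages over feeding type.
- Keep every contrast with no supplementation within EBF infants, the only group with that arm.
- Keep infants with a missing 3-month value, for example by simple baseline imputation.
- Keep Kruskal-Wallis as a sensitivity analysis.

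The cost is a change of wording on secondary outcomes. No new data are needed. The model spends one or two degrees of freedom, log-scale results must be back-transformed, and the rule for missing baselines has to be written down.
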